5.3.2 Dose/Treatment Planning Parameters

The CTV (prostate +/- SV) will be treated to minimum mean dose of 35 Gy in 5 fractions. The prescribed dose to the CTV will be 7-7.25 Gy per fraction. There will be a simultaneous integrated boost to PIRADS 3-5 or PSMA avid nodules, delivering an additional 0.5, 1.0, 1.5 or 2 Gy per fraction for a total mean dose of 37.5, 40, 42.5 or 45 Gy to the contoured nodule. The highest mean radiation dose possible (37.5, 40, 42.5 or 45 Gy) that can be delivered while respecting normal tissue constraints to rectum and urethra will be selected.

Volume of the PTV receiving prescribed SBRT dose should be $\geq 95\%$; acceptable deviation is dose $>90\%$

Critical organ limits (SBRT monotherapy):

1. Rectum: Maximum dose to 1 cc 38.5 Gy, Max dose to 3 cc 34.4 Gy,, Max point dose 40 Gy. Acceptable deviation is maximum dose to 1 cc 39 Gy, max dose to 3 cc 36 Gy and max point dose of 42 Gy.
2. Bladder: Maximum dose to 1 cc 38.5 Gy, Max point dose 40 Gy. Acceptable deviation is max point dose of 42 Gy.
3. Penile Bulb: No more than 105% of prescription dose; D3cc 25 Gy. This is a soft constraint.
4. Femoral heads: Maximum point dose 30 Gy
5. Small bowel: Maximum point dose 25 Gy
6. Urethra: Max dose 40 Gy. Will allow up to 42 Gy.

5.4 *Supportive Care Guidelines*

- a. Urinary: A proportion of patients undergoing prostate SBRT can expect increase in urinary frequency or urgency. If this becomes bothersome to the patient, medication to alleviate symptoms can be prescribed at the discretion of the treating radiation oncologist and documented in patient chart.
- b. Bowel: Bowel symptoms during time of prostate SBRT can occur. If patients develop rectal urgency, tenesmus or diarrhea, medication to alleviate symptoms can be prescribed at the discretion of the treating radiation oncologist, and documented in patient chart.

5.5 *Duration of Therapy and Criteria for Removal from Study*

In the absence of treatment delays, the SBRT is anticipated to complete within 2-3 weeks time. Patients will undergo radiation 2-3 times a week, but treatment can be slowed down to once a week at the physician's discretion; these differing fractionation patterns fall within standard of care for SBRT. Patients can be removed from the study at any point should they decide they no longer wish to participate. They will continue to receive routine medical care as necessary outside the confines of this study.

Patients will be placed in a prospective database patients undergoing prostate SBRT in our department. As per our usual care, they will fill out AUA and EPIC-26 quality of life forms at each follow up visit.

5.6 *Duration of Follow Up*

Patients will be followed as per standard care. For purposes of this study, patients will be followed with CTCAE toxicity evaluation, EPIC-26 quality of life questionnaire, AUA scores up to first follow up visit at approximately 3-6 months after completion of radiation; afterwards they will be prospectively followed as per usual care in our department with quality of life questionnaires and toxicity evaluation, AUA scores.

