1. Radiation treatment planning : Contour section 5.3.1 and 5.3.2 respectively.

- a. Select PIRADS 3-5 and/or PSMA avid (if PSMA PET/MR is available) and/or biopsy positive nodules (chosen based on physician's clinical judgment and correlation with biopsy findings)
- b. The CTV (prostate +/- SV) will be treated to dose of 35 Gy in 5 fractions. There will be a simultaneous integrated boost to PIRADS 3-5 or PSMA avid nodules, delivering at additional 0.5, 1.0, 1.5 or 2 Gy per fraction for total mean dose of 37.5, 40, 42.5 or 45 Gy to the contoured nodule.

2. Inclusion Criteria #4 :

- a. Patient must have prostate MRI with a PIRADS 3-5 lesion *or* PSMA PET with an avid intraprostatic lesion

There is no changed to the informed consent.

Summary of changes : Protocol version 2.0 10.05.2018

1. Changing the follow up from 1 month to 3-6 months
2. Radiation treatment planning – Contouring – Section 5.3.1
 - a. Select PIRADS 4-5 and/or PSMA avid (if PSMA PET/MR is available) and/or biopsy positive nodules (chosen based on physician's clinical judgment and correlation with biopsy findings) will be contoured as gross tumor volume(s) (GTV).

ICF update 10.05.2018 :

ICF was also updated to revise the follow up information from one month post RT to 3-6 months.

Protocol Summary

MRI-guided Stereotactic Body Radiotherapy (SBRT) with Simultaneous Integrated Boost for Prostate Cancer

IRB Protocol #: 1802019010

Short Title: MRI-guided prostate SBRT with Focal Boost
Principal Investigator: [name]
Sample Size: N = 30
Accrual Ceiling: This study plans to enroll a total of 30 patients
Study Population: Patients with prostate cancer with visible focal lesion on MRI
Accrual Period: 3 years
Study Design: Single-arm study for feasibility

Study Intervention Description:

Prostate SBRT: Prostate SBRT is a standard of care treatment for prostate cancer that has not spread to distant metastatic sites. Radiation is delivered to the prostate and seminal vesicles in 5 treatment sessions (fractions). Doses ranging from 35-45 Gy in 5 fractions have demonstrated good outcomes with acceptable toxicity. In this initial study, MRI guided treatment planning and delivery will be used to deliver 7-7.25 Gy to the entire prostate and seminal vesicles, with a selective boost of additional 0.5, 1.0, 1.5 or 2 Gy per fraction for total dose of 37.5, 40, 42.5 or 45 Gy to biopsy proven lesions, defined using MRI.

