2.6 ViewRay: a unique radiation delivery approach

The ViewRay MRIdian Linac system is a radiation delivery machine that integrates a linear accelerator with real-time MRI imaging. The ViewRay machine allows fusion of MR imaging with treatment planning. The uniqueness of this approach is the image guided delivery component, based on precise MRI-based detection of target and normal tissue during treatment in real-time. The ViewRay will provide real-time MRI imaging to ensure that the high-dose region is precisely targeted. MRI guided radiation has the benefit of not requiring fiducial implantation or excess radiation exposure from multiple cone beam CT. Furthermore, motion monitoring can be

performed with images acquired up to 4 frames a second, allowing live feedback of treatment position.

ViewRay offers the ideal system for delivery of prostate SBRT, due to its ability to provide image guidance “live”, during treatment. Real-time MRI imaging allows superior soft-tissue differentiation with excellent visualization of the prostate. This ViewRay platform offers the ideal setting for this study, that aims at precisely delivering prostate SBRT with a simultaneous integrated boost to visible nodules.

The goal of this study is to assess feasibility and safety of using the ViewRay to deliver prostate SBRT with SIB. Feasibility is defined as the ability to deliver treatment as planned (within the constraints defined in Section 5.3 Radiation Planning) and safety is defined as lack of acute G3 GI or GU toxicity within 30 days. The proposed SBRT dose (35-36.25 Gy in 5 fractions to the whole prostate) has been reported in the literature to be safe and well tolerated (Table 2), with no acute G3 toxicity. The proposed boost dose of an additional 0.5, 1.0, 1.5 or 2 Gy per fraction (total dose 37.5-45 Gy, depending on normal tissue constraints) is within the range of current standard of care SBRT doses, and is expected to be well-tolerated if normal tissue constraints are met. By applying rigorous normal tissue constraints and capitalizing on the imaging capability of the ViewRay we plan to deliver a treatment that is non-invasive and exceptionally precise.

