12.4 Analysis of Primary and Secondary Endpoints

Primary Endpoint:

The first primary endpoint of feasibility will be measured by the percentage of treatments that are delivered according to plan. The count and percent will be tabulated, and a 95% confidence interval estimated using an exact Clopper-Pearson binomial two-sided interval.

The second primary endpoint of safety will be measured by the percentage of treatments that do not lead to a GI/GU adverse event (defined as >Grade 3) within 30 days of treatment. The count and percent will be similarly tabulated, and a 95% confidence interval estimated using an exact Clopper-Pearson binomial two-sided interval.

Finally, the proportion of patients for whom the treatment was feasible and safe will be tabulated, and a 95% confidence interval estimated using an exact Clopper-Pearson binomial two-sided interval.

Planned sub-group analyses include feasibility, safety, and combination of both within each of the four potential target dose levels (37.5, 40, 42.5 or 45 Gy).

Secondary Endpoints:

HRQOL measures at baseline and at follow up (3-6 months post treatment start) will be summarized numerically and graphically using mean (sd), median (interquartile range), or count (percent) as appropriate, and 95% confidence intervals estimated where possible. Changes in scoring from pre- to post-treatment will also be similarly studied. EPIC overall scores as well as domain summary scores (urinary incontinence, urinary irritative/obstructive, bowel, sexual, hormonal) and individual item responses will be studied. Similarly, overall score as well as individual item responses will be studied for the AUA symptom survey.

13 Data and Safety Monitoring Plan (DSMP)

The WCMC Data and Safety Monitoring Committee (DSMC) is the central monitoring board for this study.

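### The boost increments and boost totals agree only on a 7 Gy base, but up to 7.25 Gy per fraction is permitted and the protocol does not say which of the two defines the level

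*Combined protocol and SAP*

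**What the plan says.** Section 5.3.2 gives two quantities for the prostate target. It "will be treated to minimum mean dose of 35 Gy in 5 fractions", and then "The prescribed dose to the CTV will be 7-7.25 Gy per fraction". The next sentence sets the boost for the nodule, "delivering an additional 0.5, 1.0, 1.5 or 2 Gy per fraction for a total mean dose of 37.5, 40, 42.5 or 45 Gy". The selection rule that follows uses totals only: "The highest mean radiation dose possible (37.5, 40, 42.5 or 45 Gy) that can be delivered while respecting normal tissue constraints" is the one to be chosen.

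Two other places carry the same pairing:

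- The Protocol Summary (Study Intervention Description) says the technique will "deliver 7-7.25 Gy to the entire prostate and seminal vesicles, with a selective boost of additional 0.5, 1.0, 1.5 or 2 Gy per fraction", followed by the same four totals.
- Section 2.6 refers to "The proposed SBRT dose (35-36.25 Gy in 5 fractions to the whole prostate", lists the same increments, and gives the boosted range as "total dose 37.5-45 Gy, depending on normal tissue constraints".

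The levels are then used for reporting. The primary objective (Protocol Summary and section 1.1) undertakes to count the plans achievable at each level. Sections 10 and 12.1.1 judge nodule coverage, criterion (c), by mean dose to the contoured nodule. Section 12.4 plans subgroup analyses of feasibility, safety and both combined "within each of the four potential target dose levels (37.5, 40, 42.5 or 45 Gy".

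**The concern.** A boost level is described both as an amount added to a base and as a fixed total. Both can be true only if the base is fixed, and the current text lets it vary. Above 7 Gy per fraction, a planner who follows one half of the sentence departs from the other half.

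Two things depend on this. The first is the planned nodule dose: for the same patient and nominal level, two planners could each cite 5.3.2 and arrive at different totals. The second is the meaning of a level in the results. If some patients reach a level by increment and others by total, the plan counts and the subgroup tables mix different nodule doses under one label.

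**Working it through.** **Inputs**

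- Fractions: 5 (5.3.2).
- Base b, prescribed prostate dose per fraction: 7 to 7.25 Gy (5.3.2 and Protocol Summary). As a course this is 5 × 7 = 35 Gy to 5 × 7.25 = 36.25 Gy, which matches 2.6.
- Increments i: 0.5, 1.0, 1.5 and 2.0 Gy per fraction.
- Stated totals T: 37.5, 40, 42.5 and 45 Gy, so the spacing is 2.5 Gy.

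**Step 1: reproduce the plan's figures.** With T = 5 × (b + i) and b = 7:

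- 5 × 7.5 = 37.5
- 5 × 8.0 = 40
- 5 × 8.5 = 42.5
- 5 × 9.0 = 45

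All four match. Table 1 in section 2.2 is built the same way, with columns for 7, 7.5, 8, 8.5 and 9 Gy × 5.

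**Step 2: keep the increments and vary the base.**

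| Base (Gy per fraction) | +0.5 | +1.0 | +1.5 | +2.0 | Shift, 5 × (b − 7) |
|---|---|---|---|---|---|
| 7.00 | 37.5 | 40 | 42.5 | 45 | 0 |
| 7.10 | 38.0 | 40.5 | 43.0 | 45.5 | 0.5 |
| 7.20 | 38.5 | 41.0 | 43.5 | 46.0 | 1.0 |
| 7.25 | 38.75 | 41.25 | 43.75 | 46.25 | 1.25 |

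Only b = 7 returns the stated totals.

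**Step 3: keep the totals and solve for the increment.** With i = T/5 − b and b = 7.25:

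- 7.5 − 7.25 = 0.25
- 8.0 − 7.25 = 0.75
- 8.5 − 7.25 = 1.25
- 9.0 − 7.25 = 1.75

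None of these is a listed increment.

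**Step 4: compare the shift with the level spacing.** At 7.25 Gy the shift is 1.25 / 2.5 = one half of the spacing. Three of the totals fall exactly midway between neighbouring levels: 38.75 is 1.25 Gy from both 37.5 and 40, 41.25 is 1.25 Gy from both 40 and 42.5, and 43.75 is 1.25 Gy from both 42.5 and 45. A nearest-level rule would therefore tie. The fourth, 46.25, is 1.25 Gy above the highest level and above the upper end of the range in 2.6.

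**Step 5: look for a rule that settles it.** The readable text does not say whether increment or total takes precedence above 7 Gy. It also gives no tolerance for matching an achieved mean nodule dose to a level. Section 6 (Dose Modifications) contains no rule.

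**The case against.** The strongest reply is that the total plainly governs. Every statement that selects, counts or analyses by level (Protocol Summary, 1.1, the selection sentence in 5.3.2, 10, 12.1.1 and 12.4) names it by total dose and never by increment. Sections 1.1, 5.3.2, 10 and 12.1.1 make that total a mean dose, to the nodule. On this view 38.75 to 46.25 Gy are doses the protocol never writes down, and the fault is confined to the printed increments. Much of this stands. A reader might infer that patients prescribed above 7 Gy cannot be placed in the dose levels at all, and the documents do not support that. If the total governs, every patient planned to a listed total can be placed whatever the base. Placement becomes ambiguous only if the increment governs above 7 Gy. What does not stand is that the text settles the matter: the increments appear beside the wider base in three places, including the planning section, and nothing ranks them below the totals.

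A second reply is that the increments are meant to be counted from the 35 Gy minimum mean dose rather than from the prescription, in which case all four totals follow. Section 5.3.2 permits that reading but does not state it. The Protocol Summary and 2.6 attach the boost directly to 7–7.25 Gy and to 35–36.25 Gy.

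A third reply is that the by-level tables are too small for this to matter. If 30 patients split evenly over four levels (an assumption), each has 7 or 8, and an exact 95% interval for 4 of 8 runs from about 16% to 84%. It is true that these tables will be imprecise. That does not excuse an undefined label, and it has no bearing on the planned nodule dose.

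**Conclusion.** The point holds. For any prescription above 7 Gy per fraction, the listed increments and totals contradict each other in 5.3.2, 2.6 and the Protocol Summary, by 5 × (b − 7) Gy and at most by 1.25 Gy per level. The passages must be reconciled. No view is given here on which dose is right.

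The reach is limited. It covers the planned nodule dose of patients prescribed above 7 Gy, the plan counts by level, and the subgroup tables in 12.4. A reader might go on to infer that the primary results are undermined, but the documents do not support that. The overall safety percentage needs no level assignment, and neither does overall feasibility judged against each patient's own plan. Nor does the text show that doses above 45 Gy are intended; 46.25 Gy arises only if the increment is applied to a 7.25 Gy base.

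The conclusion assumes that the increments are added to the prescribed dose, as the Protocol Summary and 2.6 present them. The share of patients prescribed above 7 Gy is not given and could be anywhere from none to all. The schema figure could not be read, so it was not checked.

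**What to change.** 1. Amend the Protocol Summary, 2.6 and 5.3.2 together so that one quantity defines the boost level: either the total mean nodule dose or the increment over a stated base. The sponsor chooses. The other quantity is derived from it, with the base written out. Check the schema for the same wording.
2. Use that single definition for the plan counts in the Protocol Summary and 1.1, for criterion (c) in 10 and 12.1.1, and for the subgroups in 12.4.
3. Record three items per patient: the base prescription, the level selected at planning and the achieved mean nodule dose.
4. Tabulate by the level selected at planning. Judge criterion (c) by comparing the achieved mean dose with that level, within a tolerance stated in advance. Levels should not be reassigned from the achieved dose, because a plan that missed its level could then be relabelled and counted as feasible.

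The cost is a wording amendment and up to three data fields. Criterion (c) already requires the mean nodule dose to be worked out, and section 11.1 already sends treatment data to REDCap. Sample size, visits and the overall analyses do not change.

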6 DOSE MODIFICATIONS

None.

7 ADVERSE EVENT REPORTING REQUIREMENTS

Adverse event (AE) monitoring and reporting is a routine part of every clinical trial. The investigator will be required to provide appropriate information concerning any findings that suggest significant hazards, contraindications, side effects, or precautions pertinent to the safe use of the drug or device under investigation. Safety will be monitored by evaluation of adverse events reported by patients or observed by investigators or research staff, as well as by other investigations such as clinical laboratory tests, x-rays, electrocardiographs, etc.

7.1 *Adverse Event Definition*

An adverse event (also referred to as an adverse experience) can be any unfavorable and unintended sign (e.g., an abnormal laboratory finding), symptom, or disease temporally associated with treatment, and does not imply any judgment about causality.

Adverse Event Characteristics and Related Attributions

CTCAE term (AE description) and grade: The descriptions and grading scales found in the revised NCI Common Terminology Criteria for Adverse Events (CTCAE) version 4.0 will be utilized for grade 3 or higher AE reporting. A copy of the CTCAE version 4.0 can be downloaded from the CTEP web site (<http://ctep.cancer.gov>).

- **Attribution** of the AE:

- Definite – The AE is *clearly related* to the study treatment.
- Probable – The AE is *likely related* to the study treatment.
- Possible – The AE *may be related* to the study treatment.
- Unlikely – The AE is *doubtfully related* to the study treatment.
- Unrelated – The AE is *clearly NOT related* to the study treatment.

7.2 *Recording of Adverse Events*

All adverse events will be recorded on a patient specific AE log. The AE log will be maintained by the research staff and kept in the patient's research chart.

7.2.1 **Reporting of AE to WCMC IRB**

All AEs occurring on this study will be reported to the IRB according to the IRB policy, which can be accessed via the following link:

http://researchintegrity.weill.cornell.edu/forms_and_policies/forms/Immediate_Reportin...

7.3 *Definition of SAE*

SAE's include death, life threatening adverse experiences, hospitalization or prolongation of hospitalization, disability or incapacitation, overdose, congenital anomalies and any other serious events that may jeopardize the subject or require medical or surgical intervention to prevent one of the outcomes listed in this definition.

7.3.1 *Reporting of SAE to IRB*

All SAEs occurring on this study will be reported to the IRB according to the IRB policy, which can be accessed via the following link:

http://researchintegrity.weill.cornell.edu/forms_and_policies/forms/Immediate_Reportin...

7.4 *Expedited Adverse Event Reporting*

The principal investigator is responsible for monitoring the safety of patients who enroll in the study. All AEs occurring after treatment will be followed until resolution. The descriptions and grading scales found in the revised NCI CTCAE version 4.0 will be used for adverse event reporting. A copy of the CTCAE version 4.0 can be downloaded from the CTEP web site (<http://ctep.cancer.gov/reporting/ctc.html>).

A serious adverse event (SAE) is any adverse experience that results in any of the following outcomes:

- Death.
- Life-threatening adverse experience.
- Requires inpatient hospitalization or prolongation of existing hospitalization.
- Persistent or significant disability/incapacity.
- A congenital anomaly/birth defect.

- Important medical events: Defined as AEs that, based upon appropriate medical judgment, may jeopardize the patient and may require medical or surgical intervention to prevent 1 of the outcomes listed above, even though these events may not be immediately life-threatening or result in death or hospitalization.

All SAEs occurring on this study will be reported to the IRB according to the IRB policy, which can be accessed via the following link:
[http://researchintegrity.weill.cornell.edu/forms_and_policies/forms/Immediate_Reportin...
Policy.pdf](http://researchintegrity.weill.cornell.edu/forms_and_policies/forms/Immediate_Reportin...)

7.4.1 AE/SAE Follow Up

All SAEs and AEs reported during this study will be followed until resolution or until the investigator confirms that the AE/SAE has stabilized and no more follow-up is required. This requirement indicates that follow-up may be required for some events after the patient discontinues participation from the study.

8 PHARMACEUTICAL INFORMATION

There is no investigative agent used on this protocol.

9 CORRELATIVE/SPECIAL STUDIES

9.1 Correlative Study: Blood draws for immune correlates and microbiome collection

Patients will have the option of having a blood draw prior to, at the completion of radiation and at 3-6 months post treatment follow up. They will also have the option of providing a stool sample for microbiome analysis at baseline, end of completion and 3-6 month follow up. This is an exploratory study where specimens will be stored for future analyses.

Blood Sample Collection and Procedure

Blood samples (40-ml) will be collected in heparinized “Green Top” tubes (for PBMC and plasma isolation) and processed within 4 h of sample receipt. The PBMC will be isolated using a 1.077 g/ml Ficoll layer to enrich the leukocytes and remove the dead cells and any red cells, and cryopreserved in 10% DMSO, 90% human AB serum at 10×10^6 cells/vial and stored in liquid nitrogen for batch analysis. Plasma will also be aliquoted and stored at -80^0C for batch analysis. We anticipate analyses of T cell subsets and neutrophil/lymphocyte ratios, as well as cytokine measurement and proliferation analyses (all markers of peripheral immune correlates to assess status over time) once funding is secured.

Microbiome collection

Collection of Specimen(s): Patients will be provided with a stool collection container and be instructed on providing a specimen appropriately, which can be done from home or in the clinic.

Handling of Specimens(s): Samples received will be promptly frozen at 20 degrees C, and transferred within the next week to a -80 degree freezer or liquid nitrogen for long-term storage. DNA extractions and 16sRNA analysis will be performed once all samples are collected.

The microbial DNA will be isolated and used to provide DNA sequence information. We will perform taxonomic characterization of bacteria (using 16S rRNA). Prokaryotic diversity will be screened using massively parallel DNA sequencing, exploiting a multiplexing technique to generate 16S rRNA sequence tags, followed by analyses (statistical, clustering, and phylogenetic) to estimate the distribution of phylotypes, differential abundance, and the relative contributions between phylotypes and community dissimilarities to the overall diversity in individuals.

We will examine whether there are metagenome sequence content changes during radiation treatment, and study whether differences in gene content indicate differences in functional pathways between the normal and irradiated microbiome using pathway analysis.

Samples will be collected by the research team and the samples will be stored in -80C freezer in [name] lab until sample analysis.

